7.6 Other Analysis Set

Not applicable.

Statistical Analysis Plan, Protocol Number V87_30

06 MAY 2022 Final Version 1.0

8. GENERAL ISSUES FOR STATISTICAL ANALYSES

8.1 Adjustment for Covariates

The main statistical analysis includes descriptive statistics for the overall population <9 years of age. Subgroup analyses will be done by age cohort (6 months to < 36 months, 3 to < 9 years). Summary tables will show unadjusted GMTs for each vaccine group by assessment.

Adjusted GMTs will be calculated based on the log-transformed antibody titers at Day 22 and Day 43 using an Analysis of Covariance (ANCOVA) model which includes the log-transformed pre-vaccination antibody titer, age cohort and vaccine group.

8.2 Handling of Dropouts, Missing Data

The distribution of subjects with reasons for missing immunogenicity values will be described by vaccine group. Key baseline characteristics, such as age and country, will be compared between the subjects with immunogenicity values and those who have missing data.

For immunogenicity data, it may be reasonable to consider missing immunogenicity values as missing completely at random (MCAR), i.e., not informative. Therefore, the immunogenicity analysis will comprise a complete case analysis only, without introducing any bias. Additional sensitivity analysis will be considered if the percentage of subjects with missing data is more than 10%.

Solicited AEs are collected using diaries from Day 1 to Day 7 post-vaccination. If the data have not been recorded for all 7 days, the assessment is considered missing and excluded from analysis. In case, at least one day is filled in but other days are missing the presence or absence of the event will be based on the available data. If more than 10% of the subjects have incomplete diary data, additional tables for solicited adverse events will be created based on complete diary card data. The number of days and number of subjects with missing data will be tabulated by vaccine group.

8.3 Multicenter Studies

The study will be conducted in two countries with a total of around 7 sites. The randomization will be stratified by site and age cohort. The effect of country and site will be explored as subgroup analysis provided that the number of enrolled subjects is sufficient.

8.4 Multiple Comparisons and Multiplicity

Statistical Analysis Plan, Protocol Number V87_30

06 MAY 2022 Final Version 1.0

This a phase 2, exploratory study and no adjustment will be applied for multiple endpoints and multiple comparisons.

8.5 Subgroups

All analyses (safety and immunogenicity) will be done by the age cohorts (6 months to < 36 months or 3 to < 9 years). Descriptive immunogenicity analysis of the GMTs will be performed by stratifying for the following subgroups:

- Sex;
- Country;
- Site.

8.6 Data Transformation

Distributions of antibodies are generally skewed to the right and approximately log-normally distributed. Therefore, prior to any statistical analysis that assumes normally distributed observations, antibody titers will be \log_{10} -transformed. GMTs and their 95% CIs will be then computed by exponentiating (base 10) the means and 95% CIs of the \log_{10} transformed titers.

8.7 Derived and Computed Variables

Demographics

In the case that Age and/or Body Mass Index must be recomputed for the statistical analysis:

Age will be calculated in months using the following formula:

$$\text{Integer } [12 * (\text{Date of Visit 1} - \text{Date of Birth} + 1) / 365.25]$$

Age will be calculated in years using the following formula:

$$\text{Integer } [(\text{Date of Visit 1} - \text{Date of Birth} + 1) / 365.25]$$

Statistical Analysis Plan, Protocol Number V87_30

06 MAY 2022 Final Version 1.0

Body Mass Index (kg/m²) will be calculated using the following formula:

$$\text{Mass (kg)} / \text{Height}^2 (\text{m}^2)$$

Immunogenicity

Values below the lower limit of quantification (LLOQ) will be set to half that limit. Values above the upper limit of quantification (ULOQ) will be set to the value of this upper limit.

Seroconversion based on **HI** antibodies is defined as binary variable for subjects with non-missing values pre-vaccination- and post-vaccination as:

= 1, if seroconverted (defined as a \geq 4-fold increase in titer post-vaccination in those with pre-vaccination titer above or equal the LLOQ (1:10), or a post-vaccination titer \geq 1:40 for subjects with pre-vaccination titer below the LLOQ (1:10))

= 0, otherwise

Seroconversion based on **MN** antibodies is defined as binary variable for subjects with non-missing values pre-vaccination- and post-vaccination as:

= 1, if seroconverted (defined as a \geq 4-fold increase in titer post-vaccination in those with pre-vaccination titer above the LLOQ, or a post-vaccination titer \geq 4 times the LLOQ for subjects with pre-vaccination titer below the LLOQ)

= 0, otherwise

Fold increase is defined as the post-vaccination titer divided by the pre-vaccination titer.

Geometric Mean Titer

The GMT will be calculated using the following formula:

Statistical Analysis Plan, Protocol Number V87_30

06 MAY 2022 Final Version 1.0

$$10^{\left\{ \frac{\sum_{i=1}^n \log_{10}(t_i)}{n} \right\}}$$

where t_1, t_2, \dots, t_n are n observed immunogenicity titers. The 95% confidence intervals for GMT will be calculated as $10^{\{M-t_{0.975,n-1}SE\}}$, $10^{\{M+t_{0.975,n-1}SE\}}$; where M and SE are the means and standard error of logarithm base 10 -transformed titers, respectively.

Solicited Adverse Events

For details see section 13.2

Unsolicited Adverse Events

All AEs will be characterized according to the date of occurrence related to the vaccination as follows:

- **Pre-vaccination (will be mapped to MH):** start date before the date of first injection of study vaccine or indicated as on injection day but before injection.
- **Emergence during vaccination phase:** all other cases.

Note: If an AE start date is missing or unknown and no indication is provided on the timing, the AE will be considered as emergent.

When start and/or end dates of an AE are only partially known, AEs will be categorized as emergent before, during, or after vaccination phase using the following rules:

- If the partial end date is before ($<$) the first vaccination (i.e., year or year & month is/are before the study vaccination year or year & month) then the AE is pre-vaccination.
- If the partial start date is equal or after (\geq) the first study vaccination (i.e., year or year & month is/are after or the same as the first study injection year or year & month) then the AE is emergent during vaccination phase.

Statistical Analysis Plan, Protocol Number V87_30

06 MAY 2022 Final Version 1.0

All AEs emergent during vaccination phase will categorized as occurring during the period of 21 days following the last vaccination based on the start date. If start date is missing or incomplete, events will be counted as yes during the period of 21 days following the last vaccination.

Adverse events that meet none of the following criteria SAE, AESI, NOCD, or AE leading to withdrawal, and had a start date more than 21 days after the last vaccination are not to be recorded. However, if recorded, these AEs should be flagged (**i.e. exclusion flag**), excluded from analysis and listed separately.

The **maximum event severity** is the greatest severity associated with a preferred term (PT) for a reported AE according to the following order: Mild < Moderate < Severe.

Vaccination-related Adverse Events are those for which the cause has been evaluated by the investigator, and recorded as possibly related, probably related or unknown/ missing.

Prior and Concomitant Medications

All medications will be characterized according to the start and end date of occurrence related to the vaccination as follows:

- **Pre-vaccination:** start date before the date of first injection of study vaccine.
- **Concomitant:** start date before vaccination but continued after vaccination or start date after vaccination. The period Day 1- 43 (i.e. 21 days after the last study vaccination) will be labeled if the start date is on or before Day 43.

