7. ASSESSMENTS

7.1 Safety Assessment

The measures of safety used in this study are routine clinical procedures. They include a close vigilance for, and stringent reporting of, selected local and systemic adverse events routinely monitored in vaccine clinical studies as indicators of reactogenicity.

An AE is defined as any untoward medical occurrence in a subject or clinical investigation subject administered a pharmaceutical product at any dose that does not necessarily have to have a causal relationship with this treatment. Therefore, an AE can be any unfavorable and unintended sign (including an abnormal laboratory finding, for example), symptom, or disease temporally associated with the use of an investigational product, whether or not considered related to the investigational product. This definition includes intercurrent illnesses or injuries and exacerbation of pre-existing conditions.

The period of observation for AEs extends from the time the subject signs informed consent /assent until he or she completes the specified safety follow-up period visit 7 (Day 387) or terminates the study early (whichever comes first). AEs occurring after the ICF/assent is signed but prior to receiving study vaccine/product will be documented as an adverse event in EDC and recorded within the source document. However, any AEs occurring prior to receipt of any study vaccine will be analyzed separately from “treatment emergent” AEs (AEs occurring after administration of the first study vaccine).

AEs are collected as either solicited or unsolicited adverse events. Solicited events are derived from organized data collection systems, such as subject diaries or interview.

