10.2 Medical History

The numbers and percentages of subjects with medical history will be presented by Medical Dictionary for Regulatory Activities (MedDRA) system organ class (SOC) and PT by vaccine group and overall. Medical history data will be tabulated for the All Enrolled, FAS, PPS and Safety Sets.

Statistical Analysis Plan, Protocol Number V87_30

06 MAY 2022 Final Version 1.0

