13.3 Unsolicited Adverse Events

This analysis applies to all ongoing solicited AEs beyond seven days after the vaccination, all unsolicited AE's occurring during the study, judged either as probably related, possibly related, or not related to vaccination by the investigator, recorded in the AE eCRF, with a start date on (but with onset after vaccination) or after the date of vaccination. AE starting prior to study vaccination will only be listed.

The original verbatim terms used by investigators to identify AEs in the eCRFs will be mapped to PTs using the MedDRA dictionary.

The AEs will then be grouped by MedDRA PTs into frequency tables according to SOC. All reported AEs, as well as AEs judged by the investigator as at least possibly related to study vaccine, will be summarized according to SOC and the PT within SOC. These summaries will be presented by the vaccination group. When an AE occurs more than once for a subject, the maximal severity and strongest relationship to the vaccine group will be counted.

The assignment to time intervals will be done by day of onset and not by days ongoing/persisting.

Statistical Analysis Plan, Protocol Number V87_30

06 MAY 2022 Final Version 1.0

The summaries will be presented by SOC and PT and different periods of onset depending on the category of events.

- From Day 1 to 21 days after the last vaccination:

- AE
- AE by maximum severity
- Related (i.e. at least possible) AE
- SAEs
- Related SAEs
- AESIs
- NOCD
- AEs leading to withdrawal (from the study or the second vaccination)
- Deaths.

- From Day 1 to end of study:

- SAEs
- Related SAEs
- AESIs
- NOCD
- AEs leading to withdrawal (from the study or the second vaccination)
- Deaths.

A summary of subjects with solicited and unsolicited non-serious treatment emergent adverse events reported by >5% of subjects sorted by system organ class and preferred term will be provided for clinicaltrials.gov and EudraCT.eu posting purposes.

Data listings of all AEs will be provided by the subject. In addition, AEs in the categories above will be provided as listed data.

Statistical Analysis Plan, Protocol Number V87_30

06 MAY 2022 Final Version 1.0

All tables will be produced overall and by age subgroup. The overview summary as well as the summary of AEs and SAEs will be also be presented by the other subgroups.

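### SAP 8.7 maps post-consent, pre-dose AEs to medical history, against the protocol and SAP 13.3, and its partial-date rule can class an event that ended before dose 1 as emergent

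*SAP*

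**What the plan says.** **SAP 8.7** sorts AEs into two classes. The first carries the label "Pre-vaccination (will be mapped to MH" and is defined by "start date before the date of first injection of study vaccine or indicated as on injection day but before injection". Everything else is emergent. Two rules cover poor dates:

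- For a missing date: "If an AE start date is missing or unknown and no indication is provided on the timing, the AE will be considered as emergent".
- For partial dates, an event is pre-vaccination if its *partial* end date falls in an earlier year, or year and month, than dose 1. It is emergent if its partial start date meets this test: "year or year & month is/are after or the same as the first study injection year or year & month".

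SAP 8.7 then counts any emergent event with a missing or incomplete start date as falling in the period up to 21 days after the last vaccination.

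**SAP 13.3** gives a different destination for pre-dose events: "AE starting prior to study vaccination will only be listed". **SAP 10.2** handles medical history: "The numbers and percentages of subjects with medical history will be presented by Medical Dictionary for Regulatory Activities" system organ class and preferred term, in the All Enrolled, FAS, PPS and Safety sets. **SAP 16** records no change to the planned analysis.

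**Protocol 7.1** requires events after consent but before vaccine to be entered as AEs, and states that "any AEs occurring prior to receipt of any study vaccine will be analyzed separately from" treatment-emergent events. Protocol 7.1.2 repeats that they are documented as AEs, and Protocol 8.4.2.1.3 says that they are only listed.

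**The concern.** Events between consent and dose 1 are not ordinary history. Consent and the baseline blood draw may take place up to 10 days before dose 1, and the draw must precede randomization (Protocol 5.1.1, 5.1.2, 5.1.5). Protocol 1.3 names risks of the draw, including fainting, infection and nerve injury. Protocol 5.1.2 sends abnormal findings at the screening assessment to the AE form. Under SAP 8.7 read with SAP 10.2, an event of this kind in a healthy child would be tabulated as baseline history. A programmer cannot tell from the SAP whether the listing in 13.3 should contain it.

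The partial-date rule raises a different worry. It can put an event known to have ended before vaccination into the tables that report unsolicited AEs after vaccination, which are a primary safety endpoint (Protocol 8.1.1.1).

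**Working it through.** The plan gives no figure to reproduce. The check is a comparison of the texts, followed by two small calculations.

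**Step 1. Trace event types through the rules.**

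| Event | Protocol 7.1, 7.1.2, 8.4.2.1.3 | SAP 13.3 | SAP 8.7 (with 10.2) |
|---|---|---|---|
| (a) Starts after consent, resolves before dose 1, dates complete | AE, analysed separately, listed | AE, listed | Medical history record, in the medical history tables |
| (b) Starts before dose 1, worsens after it, worsening entered as a new AE | In AE tables | In AE tables | Emergent, in AE tables |
| (c) Starts before dose 1, worsens after it, only the old record updated | Listed, not in tables | Listed, not in tables | Medical history record, not in AE tables |
| (d) Start day missing, month is that of dose 1, complete end date before dose 1 | Not addressed | Not addressed | Emergent, counted in the 21-day period |

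Row (a) is a contradiction that SAP 16 does not declare. In row (b) nothing is lost. In row (c) the record is outside the AE tables under all three columns, because both documents select on a start date on or after vaccination. Rows (a) to (c) therefore show that the mapping moves records between a listing and the medical history tables and changes no AE table count.

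**Step 2. Work row (d) through SAP 8.7.** Take dose 1 on the 15th, a start recorded as that month with no day, and an end date of the 12th.

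1. The end date is complete, so the partial-end-date test does not apply.
2. The partial start shares year and month with dose 1, so the event is emergent.
3. The start is incomplete, so it is counted in the 21-day period and enters the SAP 13.3 tables running from Day 1 to 21 days after the last vaccination.

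A start known only to the year behaves the same way whenever the year matches.

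**Step 3. How often a missing start day would trigger row (d).** Assume dose dates uniform over a 365-day year and onset equally likely 1 to 10 days before dose 1; both are assumptions. In a month of L days, an onset k days earlier stays in the same month for L − k dose dates.

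- Per month, summed over k = 1 to 10: 10L − 55.
- Over 12 months: 10 × 365 − 12 × 55 = 3650 − 660 = 2990.
- Share: 2990 / 3650 = 81.9%.

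So given a pre-dose onset in this window with the start day missing, about 82% share the month of dose 1. If the event also has a complete end date before dose 1, it is misclassified. The figure says nothing about how often start days are missing.

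**Step 4. Weight of one event.** With the planned 70 per arm and 35 per arm and age cohort: 1/70 = 1.4 percentage points; 1/35 = 2.9 percentage points. These apply to row (d) only.

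**The case against.** The strongest reply is that no safety data are lost. Collection is unchanged: pre-dose AEs are entered in EDC under Protocol 7.1, and all SAEs go on the AE eCRF within 24 hours under Protocol 7.1.5. Both documents also call for listings of all AEs, and nothing in SAP 8.7 forbids drawing that listing from records mapped to medical history. This stands in part. The fault is an unclear and conflicting dataset assignment, not lost data. But the SAP nowhere says the listing will be drawn that way, and the medical history tables would still mix post-consent events with true history.

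On the partial-date rule, one can argue that an end before dose 1 implies a start before dose 1, so the general definition already makes the event pre-vaccination, and that leaning towards emergent is the cautious direction for safety. The first argument shows what was probably intended. The specific rule for partial dates, however, gives the opposite answer as written. The second is sound where timing is unknown, but here the end date settles it. That the case is rare also stands: it needs a missing start day, a complete end date and resolution before dose 1.

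A reader might infer something stronger, namely that the mapping lets worsening after vaccination escape the primary safety endpoint. The documents do not support that. The protocol's AE definition covers it ("This definition includes intercurrent illnesses or injuries and exacerbation of pre-existing conditions"), so a worsening entered as a new AE has a post-dose start and is counted. A worsening kept on the old record is already excluded by the start-date rule in Protocol 8.4.2.1.3 and SAP 13.3, so deleting the mapping would not bring it in. Nor is every pre-dose AE moved: missing starts with no timing indication, and partial starts in the month or year of dose 1, go to the emergent class.

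**Conclusion.** Two limited faults hold.

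- **Mapping.** SAP 8.7 conflicts with Protocol 7.1, 7.1.2 and 8.4.2.1.3 and with SAP 13.3, without a declared change. It affects the AE listing and the four sets of medical history tables. Its effect on the primary safety numerators is nil.
- **Partial dates.** The rule misclassifies row (d) and adds such events to the 21-day AE tables. One child is 1.4 points of an arm or 2.9 points of an age-by-arm cell. The number of such events is unknown and probably very small, given a pre-dose window of at most 10 days after consent. The 82% is conditional on a missing start day and on the uniformity assumptions above.

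An analysis rule making pre-dose events emergent from the date they worsen is not part of this point. It would contradict the listing-only rule in Protocol 8.4.2.1.3 and would need dated changes in severity, which the documents do not show are collected.

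**What to change.** In SAP 8.7:

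1. Remove the medical history mapping for events that start after consent. Keep them in the AE data with a pre-vaccination flag and list them separately, as SAP 13.3 and the protocol state. Send only conditions that began before consent to medical history.
2. Let any end date before the first vaccination, complete or partial, make the event pre-vaccination whatever the start date. Compare a partial end date at the precision recorded, as now. Events whose timing stays unresolved remain emergent.
3. Optionally, state that a post-dose exacerbation is entered as a new AE with its own start date, in line with the protocol's AE definition.

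The first two cost a few lines of SAP text and a small change to the derivation, using the consent, vaccination and AE dates. They need no new data and no change to the AE analysis described in the protocol. The third is a data-entry clarification for sites.

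### The SAP counts an emergent adverse event with an incomplete start date as within 21 days of the last vaccination, even when its recorded month or year shows a later onset

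*SAP*

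**What the plan says.** SAP 8.7 (Unsolicited Adverse Events) handles dates in four steps.

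- It announces a three-way split for partly known dates: "AEs will be categorized as emergent before, during, or after vaccination phase using the following rules". Two rules follow. One makes an event pre-vaccination on the basis of its partial end date ("If the partial end date is before" the first vaccination). The other makes it emergent when the start "year or year & month is/are after or the same as the first study injection year or year & month". Neither rule defines the category after the vaccination phase.
- It then places emergent events in the post-vaccination period: "All AEs emergent during vaccination phase will categorized as occurring during the period of 21 days following the last vaccination based on the start date".
- It adds the rule at issue: "If start date is missing or incomplete, events will be counted as yes during the period of 21 days following the last vaccination".
- It defines an exclusion flag for late events that should not have been recorded. The definition begins "Adverse events that meet none of the following criteria SAE, AESI, NOCD, or AE leading to withdrawal, and had a start date more than 21", counting in days from the final dose. These are to be left out of the analysis and listed separately.

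SAP 13.3 uses two reporting periods, with assignment by day of onset: "From Day 1 to 21 days after the last vaccination" and "From Day 1 to end of study". SAEs, related SAEs, AESIs, NOCDs, AEs leading to withdrawal and deaths appear in both. The first period also has tables of all AEs, AEs by maximum severity and related AEs.

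Protocol 8.1.1.1 sets the primary endpoint for SAEs, NOCDs, AESIs and AEs leading to withdrawal over Day 1 to Day 387. The primary endpoint for any unsolicited AE covers 21 days after each vaccination.

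**The concern.** A start date with only the day missing is incomplete, so the rule applies to it. If the recorded month is well after the end of the 21-day period, the event is still counted inside, although its own date rules that out. The SAP accepts year and month as good enough evidence to call an event emergent, then sets the same evidence aside when choosing the period.

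Reporting two periods serves to distinguish early from late events. Follow-up from Day 44 to Day 387 collects SAEs, NOCDs, AESIs and AEs leading to withdrawal, and each of these has a table in the first period. Much of that follow-up is by parent interview. Protocol 5.3 schedules contacts on Days 92, 152, 202 and 387, so the last gap is 387 − 202 = 185 days. Month-only onset dates are plausible there. A misplaced event would look temporally associated with vaccination when the data show that it was not.

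**Working it through.** **1. The plan's own study days.** The second injection is on Day 22. The treatment period ends 21 days later, 22 + 21 = Day 43. Follow-up ends 365 days after the second injection, 22 + 365 = Day 387. Both agree with SAP section 3. Follow-up therefore spans 387 − 44 + 1 = 344 days.

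**2. One event traced through the rules (assumed dates).** Dose 1 is on 11 January 2021 and dose 2 on 1 February 2021, so the period closes on 22 February 2021. A chronic disease has its onset recorded as August 2021, day unknown.

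- Emergent or pre-vaccination: August 2021 is later than January 2021, so the event is emergent. The known month and year are used.
- Period: the date is incomplete, so the event is counted inside the 21-day period. The known month and year are not used.
- Truth: the earliest possible onset is 1 August 2021. That is 7 + 31 + 30 + 31 + 30 + 31 = 160 days after the period closed.

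**3. How often the known part would settle the matter.** Assume both doses on schedule, and take 1,461 consecutive calendar dates for Day 1 (from 1 July 2020). For each, count the follow-up days that lie in a later calendar month, or a later year, than the close of the period.

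| Known part of start date | Share of the 344 follow-up days recognisable as late: mean (range) | Under the SAP rule |
|---|---|---|
| Year and month | 95.7% (91.3% to 100%) | 0% |
| Year only | 47% (0% to 100%) | 0% |

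The limits in the first row can be checked by hand. The worst case is a period closing on the first of a 31-day month, which leaves 30 follow-up days in that same month: (344 − 30)/344 = 91.3%. The best case is a period closing on the last day of a month: 344/344 = 100%. Intervals of 20 or 28 days between doses gave the same results. These are shares of days, not of events.

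**4. Size of one misplaced event.** About 70 children are randomized per vaccine group and 35 per group and age cohort.

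- Per vaccine group: 1/70 = 1.4 percentage points.
- Per vaccine group and age cohort: 1/35 = 2.9 percentage points.

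**5. Which outputs are touched.**

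| Output | Affected? |
|---|---|
| SAE, AESI, NOCD, withdrawal and death tables, Day 1 to 21 days after last dose | Yes, for emergent events whose known date part is later |
| All-AE tables for the same period | Yes, by the same events; possibly also by late events outside the four categories, depending on the exclusion flag |
| Day 1 to end-of-study tables | No |
| Primary endpoint for SAE, NOCD, AESI and withdrawal, Day 1 to Day 387 | No |
| Events classed as pre-vaccination | No |

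**The case against.** The strongest reply is that the rule is a usual conservative default, applied alike to all six groups, in a descriptive study with no hypotheses and no success criterion. Subject-level listings of these categories are planned, so a rare late event can be checked individually. Controls on the data also make the trigger less likely. SAEs must be entered within 24 hours of site awareness, AESIs are handled as SAEs, medical records are reviewed, and entries are verified against source.

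Much of this stands. For a date that is wholly missing, or compatible with the period, counting the event inside is reasonable and should be kept. The controls lower the likely number of affected events, although an NOCD that is neither an SAE nor an AESI has no 24-hour rule. What does not stand is the appeal to conservatism where the known month excludes the period, because no uncertainty is left to be conservative about.

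Four stronger readings are tempting, and the documents do not support them.

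- *Every AE with an incomplete date is misplaced.* The rule covers emergent events only, and it errs only where the known part lies beyond the period.
- *The long-term primary safety result is wrong.* That endpoint runs from Day 1 to Day 387 and does not depend on the 21-day assignment. The other primary endpoint, any unsolicited AE within 21 days, can be touched, but a subject's status changes only if that child has no other AE in the period.
- *About 89% of partial dates in the study would be misassigned.* The ratio 344/387 = 0.89 is a share of calendar days. All AEs are collected up to Day 43 and only a subset afterwards, so events are not spread evenly over days.
- *The rule defeats the exclusion flag.* The flag has its own trigger, a start date more than 21 days after the last dose, and a month-only date can meet that on its face. The SAP does not say which sentence prevails. This is an ambiguity, and it matters only if an event that should not have been recorded also has an incomplete date.

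**Conclusion.** The point holds in a limited form. As written, SAP 8.7 gives a wrong period for any emergent event whose incomplete start date is nevertheless known to fall after the 21-day period. Nothing elsewhere in either document confines the rule to compatible dates. The error reaches the 21-day summaries in SAP 13.3 and stops there for SAEs, AESIs, NOCDs and AEs leading to withdrawal.

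Its practical size is unknown, because neither document gives a frequency of incomplete dates, and it may be small. Each misplaced event is worth 1.4 points per group or 2.9 points per group and age cohort. Those figures assume the planned numbers randomized; the safety-set denominators may be somewhat smaller. The handling of the exclusion flag is unclear, and the SAP should settle it.

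**What to change.** Replace the sentence in SAP 8.7 with:

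> If the start date is completely missing, or is incomplete but its known year or year and month is compatible with onset on or before 21 days after the last vaccination, the event is counted in that period. If the known part places onset after that period, the event is not counted in it.

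State in the next paragraph that the same derivation drives the exclusion flag. This also supplies the missing rule for events after the vaccination phase. An end-date condition is not needed here: an end date can show that onset was earlier, but never that it was too late for the period.

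The cost is one SAP sentence, a cross-reference and a small program change. No new data are needed. If the 21-day tables have already been produced, they would have to be rerun; the end-of-study tables would not.
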